5.2.13 Randomization Strata

Not Applicable

5.3 Conventions

QMD Ref: Worldwide-TMP-ST-054-1.0_Effective: 12Aug2022	Governing QMD: Worldwide-SOP-ST-026
Confidentiality Statement This document is the property of Worldwide Clinical Trials Inc. and may not be duplicated, copied, altered or removed from company without prior approval from Worldwide Quality Assurance or in compliance with Worldwide Standard Operating Procedures.	

Worldwide Clinical Trials Controlled Quality Management Document			
		Sponsor:	MTR-601-NHV-101
		Protocol Number:	Motric Bio
STATISTICAL ANALYSIS PLAN			

All safety data listings, summaries, figures and statistical analyses will be generated using SAS version 9.4 or higher².

Summaries will be presented by treatment cohort or overall.

Treatment labels will be displayed as follows: For SAD

Presentation 1: For on and/or after treatment summaries

MTR-601					
Placebo	Cohort 1	Cohort 2	Cohort 3	Cohort 4	Cohort 5
(N=XX)	10 mg (N=XX)	20 mg (N=XX)	40 mg (N=XX)	80 mg (N=XX)	160 mg (N=XX)
		Fast	Fed		

Presentation 2: For prior treatment summaries/histories/disposition

MTR-601					
Placebo	Cohort 1	Cohort 2	Cohort 3	Cohort 4	Cohort 5
(N=XX)	10 mg (N=XX)	20 mg (N=XX)	40 mg (N=XX)	80 mg (N=XX)	160 mg (N=XX)

Overall columns are to be included within the table shells as appropriate. Dose levels in Cohorts may be changed from the values above during the conduct of the trial based on emerging safety and PK data.

For MAD:

MTR-601						
Placebo	Cohort 1	Cohort 2	Cohort 3	Cohort 4	Cohort 5	Cohort 6
(N=XX)	10 mg (N=XX)	20 mg (N=XX)	20 mg (N=XX)	40 mg (N=XX)	80 mg (N=XX)	≤160 mg (N=XX)

The placebo participants from all cohorts in each study stage will be pooled into a single placebo (per SAD or MAD) for all summaries and presentations.

Listings will be sorted in the following order Cohort treatment, subject, parameter, and visit unless otherwise stated. All data will be listed, subjects who were not randomized will be displayed after the randomized treatment.

The 'Screening Number' will be used and represented as 'Subject Number' for all TLFs.

Continuous variables will be summarized by the number of non-missing observations, mean, median, standard deviation, and minimum and maximum.

Categorical variables will be summarized by presenting the frequency and percent. Percentages will be based on the number of subjects in the column header unless otherwise specified in the footnote. For each

QMD Ref: Worldwide-TMP-ST-054-1.0_Effective: 12Aug2022	Governing QMD: Worldwide-SOP-ST-026
Confidentiality Statement	
This document is the property of Worldwide Clinical Trials Inc. and may not be duplicated, copied, altered or removed from company without prior approval from Worldwide Quality Assurance or in compliance with Worldwide Standard Operating Procedures.	

Worldwide Clinical Trials Controlled Quality Management Document			
		Sponsor:	MTR-601-NHV-101
		Protocol Number:	Motric Bio
STATISTICAL ANALYSIS PLAN			

variable, all categories will be shown. Zero frequencies (but not the percent) within a category will be presented.

Means, medians and percentiles will be displayed to one more decimal place than the data, dispersion statistics (e.g., standard deviation) will have two more decimal places, and the minimum and maximum will be displayed to the same number of decimal places as reported in the raw data. Percentages will be displayed with one decimal place.

Derived data where it is known in advance the result will be an integer for example number of days, or study day, will be presented with zero decimal places.

PK data listings, summaries, figures, and statistical analyses will be generated using Phoenix™ WinNonlin® (Version 8.3.4 or higher)¹ or SAS (Version 9.4 or higher)². PK tables, listings, and figures will be created in WinNonlin and exported in Microsoft Word. Statistical analysis output will be created in SAS. PK concentration data will be summarized by treatment (dose level) at each nominal sample time or collection interval for SAD and by treatment (dose level) and study day at each nominal sample time or collection interval for MAD. PK parameter data will be summarized by treatment (dose level) for SAD and by treatment (dose level) and study day for MAD.

PK data (concentration-time data in all matrices) will be summarized by the number of non-missing observations (n), arithmetic mean (mean), standard deviation (SD), median, minimum (min), maximum (max), and coefficient of variation (CV%), geometric mean, and geometric CV%. PK parameter data will be summarized by n, mean, SD, median, min, max, CV%, geometric mean, and geometric mean CV%. Individual concentrations and PK parameter values will be reported to 3 significant figures. For summary statistics, n will be reported as a whole number; mean, SD, median, min, max, CV%, geometric mean, and geometric mean CV% will be reported to 3 significant figures.

P- Values will be quoted to 4 decimal places consistent with SAS PVALUEw.d format set to PVALUE6.4. P-values < 0.0001 will be presented as p<0.0001.

5.4 Subject Disposition

Subject disposition will be summarized as follows:

- The number of subjects who failed screening and the reasons for failure will be tabulated for all screened subjects.
- The number of subjects, who entered the study, were randomized and who are in each population, those who completed will be summarized by treatment cohort and overall, for all enrolled population.

QMD Ref: Worldwide-TMP-ST-054-1.0_Effective: 12Aug2022	Governing QMD: Worldwide-SOP-ST-026
Confidentiality Statement This document is the property of Worldwide Clinical Trials Inc. and may not be duplicated, copied, altered or removed from company without prior approval from Worldwide Quality Assurance or in compliance with Worldwide Standard Operating Procedures.	

Worldwide Clinical Trials Controlled Quality Management Document			
		Sponsor:	MTR-601-NHV-101
		Protocol Number:	Motric Bio
STATISTICAL ANALYSIS PLAN			

- The number of early withdrawals and the reasons for withdrawals will be tabulated by treatment cohort and overall, for the safety population.

Subjects excluded from the analysis populations and the reason for their exclusion will be summarized and listed.

5.5 Protocol Deviations

Protocol deviations will be summarized for Safety population by classification (Minor/Major). A listing of protocol deviations will be provided within Appendix 16.2 of the CSR.

5.6 Baseline Comparability

The comparability of treatment cohort with respect to subject demographics and baseline characteristics will be assessed in a descriptive manner, but no formal statistical testing will be performed. The Safety Population will be used to summarize all baseline and demographic data.

Standard continuous or categorical variable summaries will be presented by randomized treatment cohort for the following variables based on the Safety Analysis Set.

- Demographic data
- Medical history

5.7 Demographic Data

- Age at Informed Consent (years)
- Gender
- Race, where more than one race is selected the participant will be presented under the ‘Multiple races’ category in the summary but each selected race will be identified in the listing.
- Ethnicity
- Height at Screening (cm)
- Weight at Screening (kg)
- BMI at Screening (kg/m²)

5.8 Medical History

Separate tabulations of previous and ongoing conditions at screening will be presented by randomized treatment cohort and overall, for the Safety Population. Conditions will be presented by Medical Dictionary of Regulated Activities (MedDRA) primary system organ class and preferred term.

5.9 Prior and Concomitant Medications

QMD Ref: Worldwide-TMP-ST-054-1.0_Effective: 12Aug2022	Governing QMD: Worldwide-SOP-ST-026
Confidentiality Statement This document is the property of Worldwide Clinical Trials Inc. and may not be duplicated, copied, altered or removed from company without prior approval from Worldwide Quality Assurance or in compliance with Worldwide Standard Operating Procedures.	

Worldwide Clinical Trials Controlled Quality Management Document			
		Sponsor:	MTR-601-NHV-101
		Protocol Number:	Motric Bio
STATISTICAL ANALYSIS PLAN			

Separate tabulations will be produced for prior and concomitant medications presented by randomized treatment cohort and overall, for the Safety Population. Prior medications are defined as all medications starting and stopping before the date of first dose of study drug. Concomitant medications are defined as medications taken on or after the date of first dose of study drug. Concomitant medications will be summarized using Anatomic Therapeutic Chemical (ATC) Level 2. Prior and concomitant medications will be coded according to the most current version of WHO Drug Dictionary available at study start.

5.10 Substance Use

The details of the substance use will be collected at Screening and listing will be listed by each subject for Safety Population.

5.11 Exposure to Study Drug

All dosing will be listed for Safety Population.

5.12 Treatment Compliance

Not applicable.

5.13 Efficacy Analyses

Not Applicable.

5.14 Pharmacokinetic Analyses

5.14.1 Concentration-Time Data

5.14.1.1 Plasma

MRT-601 plasma concentration-time data will be tabulated by nominal time and treatment (dose level) for SAD and by nominal time, treatment (dose level), and study day for MAD using descriptive statistics. For presentation of the individual data and summary statistics, concentrations below the limit of quantitation (BLQ) will be set to zero. Nominal and relative time will be presented in hours.

MRT-601 samples will be collected at:

SAD: 0 (pre-dose) and at 0.25, 0.50, 1, 1.5, 2, 4, 6, 8, 12, 24, 48, 72, and 96 hours post-dose.

SAD (2 dose, food effect): 0 (pre-dose 1) and at 0.25, 0.50, 1, 1.5, 2, 4, 6, 8, 12, 24, 48, 72, and 96 hours postdose

MAD, Day 1: 0 (predose) and at 0.25, 0.50, 1, 1.5, 2, 4, 6, 8, and 12 hours postdose for Cohorts 1 and 2. A 24 hour sample (Day 2, predose) was added for Cohort 3 onward.

QMD Ref: Worldwide-TMP-ST-054-1.0_Effective: 12Aug2022	Governing QMD: Worldwide-SOP-ST-026
Confidentiality Statement This document is the property of Worldwide Clinical Trials Inc. and may not be duplicated, copied, altered or removed from company without prior approval from Worldwide Quality Assurance or in compliance with Worldwide Standard Operating Procedures.	

Worldwide Clinical Trials Controlled Quality Management Document			
		Sponsor:	MTR-601-NHV-101
		Protocol Number:	Motric Bio
STATISTICAL ANALYSIS PLAN			

MAD Day 7: 0 (predose) and at 0.25, 0.50, 1, 1.5, 2, 4, 6, 8, and 12 hours postdose for Cohorts 1 and 2. A 24 hour sample (Day 8, predose) was added for Cohort 3 onward.

MAD Day 14: 0 (pre-dose) and at 0.25, 0.50, 1, 1.5, 2, 4, 6, 8, 12, 24, 48, 72, and 96 hours post-dose.

Mean plasma concentration-time data will be presented graphically on linear and semi-logarithmic scales using nominal times. Individual subject concentration-time data will be presented graphically on linear and semi-logarithmic scales using actual times. For individual subject concentration-time data, spaghetti plots (all subjects in one plot per treatment) and all treatments in one plot for each subject will be created.

For SAD, mean profiles and spaghetti plots will be created.

For SAD (food effect): mean profiles, spaghetti plots, and individual plots (fed vs. fasted) will be created.

For MAD: mean profiles comparing doses on Days 1, 7, and 14, mean profiles comparing study days per dose level, spaghetti plots (by dose level and study day), and individual plots comparing study days for each subject will be created.

The PK Population will be used in the tabulation of concentration-time data and in the creation of concentration-time profiles. The Safety Population will be used for the concentration-time listings.

5.14.1.2 Urine

MRT-601 concentration-time data in urine will be tabulated by dose level, study day, and collection interval using descriptive statistics. For presentation of the individual data and summary statistics, concentrations below the limit of quantification (BLQ) will be set to zero.

Urine collection times are:

SAD: from a pre-dose void and post-dose from 0–4 hours, 4–8 hours, 8–12 hours, and 12–24 hours; from 24–48 hours post-dose (Day 2); from 48–72 hours post-dose (Day 3); and from 72–96 hours post-dose (Day 4).

MAD (Day 1): from a pre-dose void and post-dose from 0–4 hours, 4–8 hours, 8–12 hours and 12–24 hours post-dose.

MAD (Day 7): from a pre-dose void and post-dose from 0–4 hours, 4–8 hours, 8–12 hours, and 12–24 hours post dose

MAD (Day 14): from a pre-dose void and post-dose from 0–4 hours, 4–8 hours, 8–12 hours, 12–24 hours, 24–48 hours, 48–72 hours, and 72–96 hours post dose.

5.14.2 Pharmacokinetic Methodology

QMD Ref: Worldwide-TMP-ST-054-1.0_Effective: 12Aug2022	Governing QMD: Worldwide-SOP-ST-026
Confidentiality Statement This document is the property of Worldwide Clinical Trials Inc. and may not be duplicated, copied, altered or removed from company without prior approval from Worldwide Quality Assurance or in compliance with Worldwide Standard Operating Procedures.	

Worldwide Clinical Trials Controlled Quality Management Document			
		Sponsor:	MTR-601-NHV-101
		Protocol Number:	Motric Bio
STATISTICAL ANALYSIS PLAN			

Concentration-time data for MRT-601 in plasma will be analyzed using noncompartmental methods in Phoenix™ WinNonlin® (Version 8.3.4 or higher, Certara, L.P.)² in conjunction with Certara Integral™ (Version 23.10.1, Certara, USA, Inc.)³. The PK Population will be used in the PK analysis.

During the PK analysis, concentrations below the limit of quantification (BLQ) up to the time of the first quantifiable concentration will be treated as zero. Embedded (values between 2 quantifiable concentrations) and terminal BLQ concentrations will be treated as “missing”. Calculation of the PK characteristics will be based on actual elapsed times [h] relative to dosing.

Lambda-z (λ_z) and AUC_{inf} Reporting Criteria

The following criteria will be used to report λ_z :

- At least three quantifiable concentrations will be used in the regression
- C_{max} or data prior to C_{max} will not be included in the regression.
- The adjusted regression coefficient (R² adj) should be ≥ 0.80 .

If these acceptance criteria are not met, λ_z reported for individual subjects will be retained in PK parameter tables for informational purposes; λ_z will be excluded from summary statistics. Parameters calculated using λ_z (T_{1/2}, CL/F, V_z/F) will be reported as ND (not determinable). Lambda-z (λ_z) and descriptive parameters (λ_z time range, Adj R², etc.) will be presented in a separate listing.

If lambda-z acceptance criteria are met and AUC_{inf} is estimable, the following criteria are used to report AUC_{inf}:

- The percentage of AUC_{inf} based on extrapolation should be <30.0%.

If the percentage of AUC_{inf} based on extrapolation is 30.0% or greater, AUC_{inf} and AUC_{Extrap} will be retained in a PK parameter table for informational purposes; these parameters will be excluded from summary statistics, subsequent PK calculations (e.g., CL/F, and V_z/F), and statistical analysis (e.g., ANOVA).

At least 3 consecutive quantifiable concentrations are required to estimate AUC_{last}. If a PK profile has at least 1 quantifiable concentration, then C_{max}, and T_{max} will be reported; other parameters will be reported as missing (ND).

5.14.3 Statistical Analysis

QMD Ref: Worldwide-TMP-ST-054-1.0_Effective: 12Aug2022	Governing QMD: Worldwide-SOP-ST-026
Confidentiality Statement This document is the property of Worldwide Clinical Trials Inc. and may not be duplicated, copied, altered or removed from company without prior approval from Worldwide Quality Assurance or in compliance with Worldwide Standard Operating Procedures.	

Worldwide Clinical Trials Controlled Quality Management Document			
		Sponsor:	MTR-601-NHV-101
		Protocol Number:	Motric Bio
STATISTICAL ANALYSIS PLAN			

5.14.3.1 Dose Proportionality

The pharmacokinetic parameters for C_{\max} , AUC_{last} , and AUC_{inf} (SAD); C_{\max} (MAD, Day 1 and Day 7); and $C_{\max, \text{ss}}$ and AUC_{tau} (MAD, Day 14) will be compared across doses to assess dose proportionality (i.e., proportionality of a change in systemic exposure with a change in dose). Statistical analyses will be done using a power model (Smith, 2000)⁴ of the following general form,

$$\ln(\text{PK}) = \ln(\beta_0) + \beta_1 \cdot \ln(\text{Dose}) + \epsilon,$$

Where

PK is the pharmacokinetic parameter tested (e.g. C_{\max} or AUC)

$\ln(\beta_0)$ is the y-intercept,

β_1 is the slope (a value of $\beta_1 \approx 1$ indicates linearity), and

ϵ is an error term

The estimate of β_1 with the 90% CIs will be reported along with the associated p-value and the dose range for proportionality. Dose proportionality plots will be created as well.

5.14.3.2 Food Effect (SAD, 2 Dose)

As all treatments for SAD and MAD study parts are administered under fed conditions, a comparison of fasted and fed C_{\max} , AUC_{last} , and AUC_{inf} will be performed.

Analyses of variance (ANOVA) will be performed on the natural log transformed AUC_{last} , AUC_{inf} , and C_{\max} using MIXED procedure in SAS. The MIXED model will contain treatment as a fixed effect. The geometric mean ratios (Test (Fasted-Period 1)/Reference (Fed-Period 2)) and their 90% confidence intervals will be provided.

The Wilcoxon signed rank test will be used for a nonparametric comparison of T_{\max} values; a significant difference is defined a priori as $p < 0.05$.

Conclusions regarding the results of the statistical analysis (ANOVA) of PK parameters across treatments will be based on the ratio of the geometric means (Test / Reference) and the 90% confidence interval about the ratio. No significant difference will be demonstrated if the 90% confidence intervals are fully contained within the limits of 80.00% to 125.00%.

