1 INTRODUCTION

This document details the planned statistical analyses for Motric Bio, protocol “MTR-601-NHV-101” study titled “A Randomized, Double-Blind, Placebo-Controlled, First-in-Human, Single and Multiple Ascending Dose Study of MTR-601 in Healthy Volunteers”.

The proposed analyses are based on the contents of the final version 4.0 of the protocol (dated 15-Apr-2024). Exploratory parameters/endpoints will be documented separately in standalone report.

This is a phase 1, randomized, double blind, placebo-controlled, FIH (first in human) study of MTR-601 in normal healthy volunteers will consist of 5 single ascending dose (SAD) level cohorts (including 1 SAD Level 2 Two-Dose cohort), and up to 6 multiple ascending dose (MAD) level cohorts, each comprised of 8 subjects (6 MTR-601; 2 placebo). The current study is a FIH evaluation of MTR-601 and focuses on the safety, tolerability, and pharmacokinetics (including uptake into skeletal muscle) of the drug in normal healthy volunteers. Exploratory assessments of effects on the force of muscular contraction will also be performed and evaluated as it relates to dose, exposure, and/or muscle accumulation with potential adjustments for total body muscle mass.

As a FIH study, this will be conducted in normal healthy volunteers in the fed state, with further evaluation of food effect in SAD dose level 2, as nonclinical studies have indicated that food increases drug exposure. The evaluations of effects on muscular contraction with potential adjustments for total body muscle mass will help guide dosing selection in adult and potential pediatric patient populations in subsequent clinical studies.

The total sample size will be up to 88 subjects to accommodate withdrawal of consent or replacement for other non-TEAE reasons.

QMD Ref: Worldwide-TMP-ST-054-1.0_Effective: 12Aug2022	Governing QMD: Worldwide-SOP-ST-026
Confidentiality Statement This document is the property of Worldwide Clinical Trials Inc. and may not be duplicated, copied, altered or removed from company without prior approval from Worldwide Quality Assurance or in compliance with Worldwide Standard Operating Procedures.	

Worldwide Clinical Trials Controlled Quality Management Document				
			Sponsor:	MTR-601-NHV-101
			Protocol Number:	Motric Bio
STATISTICAL ANALYSIS PLAN				

SAD/MAD Dose Level Cohorts

SAD/MAD Dose Level Cohorts ^a				
SAD/MAD Cohort ^{a & b}	Dose ^g	Fasted	Fed Standard ^c	N ^e
SAD Level 1	10 mg		✓	8 ^f

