5.1.4 Pharmacokinetic (PK) Population

Includes all subjects who received study treatment and have sufficient MTR-601 plasma concentration data to estimate at least one of the planned PK parameters. All such subjects will be evaluated for PK unless major protocol deviations may have affected the data or if key dosing information is missing. This is the primary population for PK analysis.

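### The food-effect model names no subject term, so run as written it treats paired fasted and fed data as independent and its 90% interval over-covers

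*SAP*

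**What the plan says.** SAP 5.14.3.2 compares fasted with fed exposure in the SAD Level 2, Two-Dose cohort. An ANOVA of ln(AUClast), ln(AUCinf) and ln(Cmax) is run "using MIXED procedure in SAS", and the model statement reads "The MIXED model will contain treatment as a fixed effect". No subject effect, repeated-measures statement or covariance structure is named there or in any other section.

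The contrast is by period: "The geometric mean ratios (Test (Fasted-Period 1)/Reference (Fed-Period 2)) and their 90% confidence intervals will be provided". The decision rule is "No significant difference will be demonstrated if the 90% confidence intervals are fully contained within the limits of" 80.00% to 125.00%.

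The design is paired. Protocol 4.1 doses the Level 2 subjects fasted on Day 1 and, after a 4-day washout, fed on Day 6. SAP 1 describes the cohorts as "each comprised of 8 subjects (6 MTR-601; 2 placebo"), and SAP 5.1.4 limits the PK population to subjects who "have sufficient MTR-601 plasma concentration data to estimate at least one of the planned PK parameters". Placebo subjects therefore drop out and at most six pairs remain. AUCinf may have fewer, because SAP 5.14.2 removes values with 30.0% or more extrapolation from the ANOVA.

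For Tmax the same section does use the pairing: "The Wilcoxon signed rank test will be used for a nonparametric comparison of" the two conditions.

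**The concern.** A model with treatment alone treats 12 observations from six people as 12 independent observations. Differences between subjects, which cancel when each subject is compared with himself or herself, stay in the error term. The interval then no longer has its stated 90% level.

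SAP 5.14.3.2 bases its conclusion on this interval. Pairing is the main source of precision with six subjects, and losing it makes the 80.00–125.00% rule much harder to meet when food has no effect.

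**Working it through.** The plan states no interval width, CV or power for the food effect, so there is no figure of its own to reproduce.

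**Inputs from the documents.** Six MTR-601 subjects, each dosed twice (Protocol 4.1, SAP 1); 90% interval; limits 80.00–125.00%; treatment as the only named model term (SAP 5.14.3.2).

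**Assumptions.** Between-subject CV 10–50% and within-subject CV 15–30%, since the documents give none. Log-scale variances are ln(1 + CV²): 0.0100 at 10%, 0.0223 at 15%, 0.0392 at 20%, 0.0862 at 30%, 0.1484 at 40%, 0.2231 at 50%. Write sB² and sW² for the between- and within-subject variances, and rho = sB²/(sB² + sW²).

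**Formulas for the half-width on the log scale.**
- As written, 10 df: 1.812 × √[2(sB² + sW²)/6]
- Paired, 5 df: 2.015 × √[2 sW²/6]

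**Example at 20/20% (between/within).** As written: 1.812 × √(2 × 0.0784/6) = 0.293. Paired: 2.015 × √(2 × 0.0392/6) = 0.230. The ratio is 1.27.

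| Between/within CV | rho | Half-width as written | Half-width paired | Ratio | 90% CI at observed ratio 1, as written | Paired |
|---|---|---|---|---|---|---|
| 10/20% | 0.20 | 0.232 | 0.230 | 1.01 | 79.3–126.1% | 79.4–125.9% |
| 20/20% | 0.50 | 0.293 | 0.230 | 1.27 | 74.6–134.1% | 79.4–125.9% |
| 40/20% | 0.79 | 0.453 | 0.230 | 1.97 | 63.6–157.3% | 79.4–125.9% |
| 30/15% | 0.79 | 0.345 | 0.173 | 1.99 | 70.9–141.1% | 84.1–119.0% |
| 50/15% | 0.91 | 0.518 | 0.173 | 2.99 | 59.5–167.9% | 84.1–119.0% |

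**Break-even.** The ratio of half-widths is (1.812/2.015)/√(1 − rho). It equals 1 at rho = 1 − (1.812/2.015)² = 0.19. At rho = 0 it is 0.90, so the unpaired interval would be about 10% narrower. Break-even rises to 0.24 with five pairs and 0.32 with four.

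**Coverage of the nominal 90% interval as written (simulation).** About 93% at 10/20%, 97% at 20/20% and 99.4% at 40/20%. The paired interval stays at about 90%.

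**The SAP's own rule at a true ratio of 1 (simulation).** Chance that the interval lies within 80.00–125.00%:
- 20/20%: 4.4% as written, about 19% paired
- 40/20%: 0.5% as written, about 19% paired
- 30/15%: 3.6% as written, about 47% paired

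**Direction of the error.** With complete pairs the two models give the same geometric mean ratio. Over-coverage can only lower the chance of containment when the true ratio lies at or outside a limit. At a true ratio of 0.7 with 40/20%, containment is 0.01% as written and 0.34% paired.

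**The case against.** **The SAP omits a subject term; it does not exclude one.** The sentence lists a fixed effect and does not say there are no others. The period labels, the signed rank test for Tmax and the individual fed-versus-fasted plots in SAP 5.14.1.1 all suggest that a within-subject analysis was intended. This stands as far as intent goes, so a reader should not infer that the sponsor chose an unpaired analysis. It does not repair the text: a programmer who codes the named term gets the wrong interval. The table carrying this analysis (14.4.11.1) is checked by manual review, not independent programming.

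**The width claim is conditional.** This stands. Over-coverage needs only a positive correlation, but a wider interval on average needs more than about 0.19, and the documents give no estimate. At 10/20% the two intervals are nearly equal.

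**A reader might infer that a real food effect would be missed because the interval includes 1.** The documents do not support this. SAP 5.14.3.2 never uses exclusion of 1; its only interval criterion is containment in 80.00–125.00%. At a true ratio of 0.7, no difference is almost never declared under either model.

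**The stakes are modest.** The study is not powered (Protocol 9.4), food effect is not among the PK endpoints listed in SAP 2, every other cohort is dosed fed, and the escalation ceiling is an absolute Cmax and AUC limit. This stands and limits the harm. It does not justify a named model whose 90% interval is not a 90% interval.

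**Tmax.** The smallest exact two-sided signed rank p is 2/2⁶ = 0.031 with six pairs and 2/2⁵ = 0.0625 with five, so one lost or tied pair puts p < 0.05 out of reach. That is worth knowing when the result is read. Replacing the test is a matter of preference, not a required change.

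**Conclusion.** The model in SAP 5.14.3.2 is wrong as written for this design. Its nominal 90% interval over-covers whenever a subject's two values are positively correlated. For between-subject CVs of 20–50% and within-subject CVs of 15–30%, all assumed, the log half-width is 1.09 to 2.99 times the paired one. The main cost falls on the SAP's own rule when food has no effect: containment drops from about 19% to 4.4% at 20/20% and to 0.5% at 40/20%.

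The error is conservative. It does not raise the rate of false conclusions of no difference, and it leaves the ratio unchanged when pairs are complete.

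Correcting the model does not make the comparison precise. At a within-subject CV of 20% and a true ratio of 1, about 81% of trials would still fail containment with six pairs. Nor does it separate food from period, because every subject is dosed fasted first.

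**What to change.** Replace the model sentence in SAP 5.14.3.2 with: *The MIXED model for each log-transformed parameter will contain treatment and subject as fixed effects; a subject with a value in only one period does not contribute to the ratio.* This is the paired t analysis of log differences. It also settles how a subject with only one usable AUCinf is handled. Subject as a fixed effect is preferable to a random one here: the random-effect version matches the paired analysis only with complete pairs and a positive estimate of the subject variance.

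Add one sentence saying that food and period are confounded by the fixed order, so the ratio cannot be attributed to food alone and a period term cannot be estimated.

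The cost is two sentences and one changed line of SAS code, with no new data. SAP 5 requires approval before database lock; after that, an addendum is needed. The statistical price is 5 error degrees of freedom in place of 10, so the interval would be slightly wider (about 11% on the log scale, 2.015/1.812) if the within-subject correlation were near zero.

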9. STATISTICAL CONSIDERATIONS

9.1. Statistical Hypotheses

No formal statistical hypotheses testing will be performed.

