4 RANDOMIZATION

SAD cohorts:

- For each cohort (Level 1-5), 6 subjects will be randomized to receive MTR-601 and 2 subjects will be randomized to receive placebo.
- The SAD cohorts will be randomized 1:1 for sentinels and remaining 6 subjects in each cohort will be randomized 5:1 to receive MTR-601 or placebo. All SAD dose cohorts (including Level 2, Two-Dose) will have 2 sentinel subjects followed at least 72 hours later by the remaining 6 subjects.

In addition to the randomization scheme, there are also some specific instructions for the SAD Level 2, Two-Dose level cohort:

- For the first dose, subjects will be fasting.
- For the second dose, subjects will be fed state (standard not-high fat breakfast) 30 minutes before dosing.

MAD cohorts:

- For each cohort (Level 1-6), 6 subjects will be randomized to receive MTR-601 and 2 subjects will be randomized to receive placebo.

There are no sentinels in the MAD cohorts.

Cohort Type	Sentinels	Remaining Subjects
SAD	1:1	5:1
MAD	0	6:2

Subjects will be assigned to randomized treatment by the unblinded pharmacist in a sequential manner using the pre-determined randomization schedule. Subjects, the Sponsor study team, and the Investigator/site staff will be blinded to treatment assignment until after the final subject has completed the study. Unblinded personnel include site pharmacist (or designee), the unblinded pharmacy monitor (to ensure study drug accountability), and the Sponsor's unblinded team.

QMD Ref: Worldwide-TMP-ST-054-1.0_Effective: 12Aug2022	Governing QMD: Worldwide-SOP-ST-026
Confidentiality Statement This document is the property of Worldwide Clinical Trials Inc. and may not be duplicated, copied, altered or removed from company without prior approval from Worldwide Quality Assurance or in compliance with Worldwide Standard Operating Procedures.	

Worldwide Clinical Trials Controlled Quality Management Document			
		Sponsor:	MTR-601-NHV-101
		Protocol Number:	Motric Bio
STATISTICAL ANALYSIS PLAN			

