8 CHANGES TO PLANNED PROTOCOL ANALYSIS

There are no changes to the planned protocol analysis.

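### The Tmax food effect is judged only by a signed-rank test at p < 0.05 in at most six subjects, with no paired estimate or interval, so a non-significant result is uninformative

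*SAP*

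**What the plan says.** SAP 5.14.3.2 compares the fasted (Period 1) and fed (Period 2) doses of SAD Level 2. Log-transformed Cmax, AUClast and AUCinf go into a mixed model and are reported as geometric mean ratios with 90% confidence intervals, read against 80.00% to 125.00%. Tmax is handled separately: "The Wilcoxon signed rank test will be used for a nonparametric comparison of T_{\max} values; a significant difference is defined a priori as $p <" (the threshold is 0.05). The section gives no sidedness, no choice between exact and approximate p-values, no rule for zero differences, and no estimate or interval for the Tmax shift.

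The number of pairs follows from SAP 4: "For each cohort (Level 1-5), 6 subjects will be randomized to receive MTR-601 and 2 subjects will be randomized to receive placebo". SAP 5.1.4 limits the PK Population to subjects with "sufficient MTR-601 plasma concentration data to estimate at least one of the planned PK parameters", so the placebo subjects add no pairs. Under SAP 5.14.2, PK parameters are calculated from actual elapsed times.

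Other Tmax output is descriptive. SAP 5.3 reports individual parameter values and summarizes them by treatment, including median, minimum and maximum. Table 14.4.11.1, the food-effect table, is titled for log-transformed parameters only.

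**The concern.** A signed-rank test on six pairs has very few attainable p-values, so a 0.05 threshold acts as a near-unanimity rule. If that threshold is the only stated criterion for Tmax, a non-significant result says little about whether food delays the peak. Without an interval, the report does not show how large a delay the data still allow. Five usable pairs are foreseeable: Protocol 7.3 does not replace subjects withdrawn for adverse events, and SAP 5.1.4 allows profiles affected by major deviations to be excluded. Because the version of the test is left open, the significance call could also depend on a choice made after the data are seen.

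**Working it through.** **Inputs.**
- Pairs: SAP 4 states "The SAD cohorts will be randomized 1:1 for sentinels and remaining 6 subjects in each cohort will be randomized 5:1". That gives 1 active sentinel + 5 active subjects = 6 on MTR-601 and 1 + 1 = 2 on placebo, which reproduces the plan's 6 and 2. At most six pairs are therefore planned.
- Threshold: p < 0.05 (SAP 5.14.3.2).
- The documents give no power calculation for this test and no Tmax variability.

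**Exact two-sided p-values.** Under the null hypothesis all 2^n sign patterns are equally likely. With W the smaller rank sum, p = 2 × (number of patterns with rank sum ≤ W) / 2^n.

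| Pairs | W = 0 (all the same way) | W = 1 (smallest shift opposite) | W = 2 |
|---|---|---|---|
| 6 | 2/64 = 0.031 | 4/64 = 0.0625 | 6/64 = 0.094 |
| 5 | 2/32 = 0.0625 | 4/32 = 0.125 | 6/32 = 0.188 |

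Tied absolute differences do not change this. Over every tie pattern with mid-ranks, six pairs with at least one opposite shift give p of at least 0.0625, and five pairs never go below 0.0625.

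**Power with six non-zero pairs.** Let q be the assumed chance that a subject shifts in the majority direction. Significance needs unanimity, so power = q^6 + (1 − q)^6.
- q = 0.7: 0.1176 + 0.0007 = 0.118
- q = 0.8: 0.2621 + 0.0001 = 0.262
- q = 0.9: 0.531
- q = 0.95: 0.735

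With five pairs, power is zero for any effect.

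**Dependence on the unspecified version.** The normal approximation uses mean n(n+1)/4 and variance n(n+1)(2n+1)/24.
- Five pairs, W = 0: mean 7.5, SD √13.75 = 3.708. Uncorrected, z = 7.5/3.708 = 2.02 and p = 0.043. With continuity correction, z = 7.0/3.708 = 1.89 and p = 0.059.
- Six pairs, W = 1: mean 10.5, SD √22.75 = 4.770. Uncorrected, z = 9.5/4.770 = 1.99 and p = 0.046. Corrected, z = 9.0/4.770 = 1.89 and p = 0.059.
- A one-sided exact test halves the table entries, so five unanimous pairs give 0.031, and six pairs are significant at W = 1 (0.031) and W = 2 (0.047).

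The continuity-corrected approximation makes the same decisions as the two-sided exact test. The uncorrected and one-sided versions do not.

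**Level of the proposed interval.** The Hodges-Lehmann interval runs between ordered averages of pairs of differences, each difference paired with itself included. With six pairs, third smallest to third largest has level 1 − 6/64 = 90.6%. With five, smallest to largest has level 1 − 2/32 = 93.8%.

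**The case against.** The strongest reply is that this is a supportive comparison in a study that Protocol 9.4 calls non-powered. The opening sentence of SAP 5.14.3.2 names Cmax, AUClast and AUCinf as the food-effect comparison. The protocol attributes fed dosing to nonclinical exposure data (sections 1.2 and 2.4), not to Tmax. Individual values and fasted-versus-fed profiles are planned, so a reader could work out each paired shift by hand. All of this stands and limits the impact. It does not supply a planned paired estimate or a measure of its precision.

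Several stronger readings are tempting and are not supported:
- **That the sponsor will read non-significance as no Tmax effect.** The SAP only defines what counts as a significant difference. Its wording about demonstrating no significant difference belongs to the 90% CI rule for the ANOVA parameters. The gap is that the SAP is silent for Tmax.
- **That p < 0.05 can only come from a unanimous shift and never from five pairs, without qualification.** This holds for the two-sided exact version. Two-sided is the natural reading of a non-directional difference, but the SAP does not say so.
- **That zero differences from the coarse sampling grid will cripple the test.** SAP 5.14.2 uses actual elapsed times, so exact zeros should be uncommon.
- **That almost any realistic food effect would be missed.** In a simulation with assumed log-normal Tmax on the planned sampling times (between-subject log-SD 0.25, within-subject log-SD 0.3 to 0.5, actual times with 1-minute SD jitter), a median moving from 2 h to 4 h is significant in about 56% to 30% of trials. For 2 h to 6 h the range is 91% to 63%, and for 2 h to 8 h it is 98% to 81%. Large shifts would often be found.

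There is also a fair objection to deleting the test. Protocol 2.3 and SAP 6 show that unblinded data including this cohort have already been reviewed by the sponsor team, so a prespecified test should be supplemented, not removed.

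**Conclusion.** The point holds as a cheap improvement. The only stated Tmax criterion is a threshold that, in its two-sided exact form, needs all six subjects to shift the same way and cannot be met with five pairs. Power is about 26% at q = 0.8 and 53% at q = 0.9. These q values are assumptions, because the documents give no Tmax data. A non-significant result is therefore uninformative, and the plan offers no paired estimate or interval to put in its place. Leaving the test version open is a defect in itself: the same five unanimous pairs give 0.0625 or 0.043.

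Protocol 9.1 says "No formal statistical hypotheses testing will be performed" and SAP 8 says "There are no changes to the planned protocol analysis", which sits awkwardly with a significance threshold. A reader might infer that correcting the Tmax rule removes that conflict. It does not, because SAP 5.14.3.1 also reports a p-value, so that matter is separate.

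**What to change.** In SAP 5.14.3.2:
1. Make the primary Tmax summary the Hodges-Lehmann median of the within-subject fed-minus-fasted differences, from actual elapsed times as in SAP 5.14.2, with its exact distribution-free interval (90.6% with six pairs, 93.8% with five). List the individual differences. Label the direction clearly, because the Cmax and AUC ratios run fasted over fed.
2. Keep the signed-rank test as supportive only, stated as two-sided and exact, with a rule for zero differences.
3. State that a non-significant result will not be taken as absence of a Tmax effect.
4. Add the estimate and interval to Table 14.4.11.1, with its title widened, or to a companion table.

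Record the change as made after the unblinded review. The cost is one SAP paragraph and one table row, with no new data, subjects or procedures. The interval will be wide, and with five pairs it is simply the range from the smallest to the largest individual difference.
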